## 10.0 Statistical Considerations

### 10.1 Preliminary Analyses

Premature Termination. Patients will be considered dropouts (a) if they miss two or more sessions or (b) if serious adverse reactions or clinical complications (e.g., suicidal intention) develop. Initial data analyses will be conducted on treatment completers. This will address relative efficacy among treatment completers. A second analysis will be conducted including all patients who initiate treatment using an intent-to-treat analysis. This will address relative efficacy in the population intended for treatment, thus incorporating issues related to potential differential dropouts in the treatment groups. Finally, analyses will be conducted to see if treatment completers differ from drop-outs on demographic variables and pre-treatment measures.

Group Equivalence. We will evaluate the effectiveness of random assignment to two treatment groups by comparing the groups on demographics, baseline measures of key outcome variables, and other important theoretical covariates. We will characterize differences between study dropouts and completers, and between dropouts from the VRE+DEX and VRE+placebo groups. We will compare dropouts to completers on the same set of baseline variables that will be used to examine initial group equivalence. Differences between conditions will be assessed using one way ANOVA for continuous variables and chi-square analyses for categorical variables (Fleiss et al., 2013). Any observed differences that approach statistical significance ( $P \leq 0.15$ ), and which are theoretically or empirically identified as potential confounders will be included as covariates in subsequent cross sectional and longitudinal analyses.

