### 10.2 Statistical Analyses

#### Power and Sample Size

Power calculations are based on Cohen (1992). We set the Type I Error rate at 0.05 (two-tailed) for all computations. We first calculated the number of participants needed to test the effect of VRE augmentation with DEX at immediate post-treatment assessment (Hypothesis 1 above). Then, knowing how many participants would be needed at the end of this phase, we worked backward to calculate how many participants would need to be enrolled initially. We will continue to collect data from all participants, including those who drop out of treatment or are discontinued. Thus, loss to the study represents a failure to participate in measurement, and not merely dropout from treatment. We assumed that: (1) 10% of participants will be lost to the

study by the end of treatment; an additional 15% of participants will drop out of treatment, resulting in 25% of participants randomized to placebo or 0.5mg DEX groups that would not complete treatment. We anticipate that 10% of completers will be lost to the study prior to the 3 month follow-up visits.

The effect size measure used,  $d$ , represents the standardized difference between sample means. Cohen (1988) has proposed that  $d = .30$ ,  $.50$ , and  $.80$  be categorized as “small,” “medium,” and “large,” respectively. We assume that a medium effect size—half a standard deviation—is the smallest clinically meaningful difference between DEX-augmented VRE vs. placebo-augmented VRE at the end of treatment.

For a two-group study design, 100 participants ( $n=50$  in each group) would be needed to achieve a minimum desired power of 85% to detect an effect size of  $.65$  with a 2-sided test at a significance level of 0.05.

Hypothesis 1: Patients who receive VRE+DEX will evidence more improvement on within-session measures (SUDs), on immediate post-treatment symptoms measures and on startle, SCR and HR, than the group who receives placebo.

To analyze pre-treatment and immediate post-treatment differences, the first analysis will compare the VRE+DEX condition to the VRE+placebo condition on the following outcome measures: 1) symptom measures (continuous variables); 2) psychophysiological measures (startle responses, cortisol levels, heart-rate, skin conductance) (continuous variables). It is expected that VRE+DEX participants will show significant improvement on all outcome measures immediately post-treatment compared to VRE+ placebo participants.

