Continuous variables will be analyzed using multivariate repeated measures ANCOVA with treatment condition being the between subjects factor, the pre-treatment vs. post-treatment condition being the within subjects factor, and the scale scores as the multiple measures accounting for appropriate covariates as determined through preliminary analyses discussed above. Adjusted means and mean differences as well as interaction terms will be obtained and evaluated. Categorical variables will be analyzed using logistic regression and controlling for appropriate covariates resulting in adjusted odd ratios.

An additional approach to testing this hypothesis will involve using two categorical measures of clinically significant improvement: 1) a 30% decrease in the CAPs, and 2) a rating of “much improved” or “very much improved” by the therapist and participant on the CGI inventory at the end of active treatment. These data will be analyzed using logistic regression with the inclusion of appropriate terms for the covariates and treatment-by-covariate interactions.

Furthermore, we will look at the number of sessions required to reach 70% improvement or maximum treatment response and the number of dropouts, predicting fewer sessions to reach 70% improvement or maximum treatment response and fewer dropouts in the VRE + DEX group.

Within-subject measures will also be obtained to assess improvement within sessions. SUDS and psychophysiological measures (heart rate and skin conductance) will be used to measure within session anxiety levels. Average and peak values of these continuous variables will also be analyzed using a repeated measures ANCOVA.

Hypothesis 2: Patients who receive VRE+DEX will evidence more improvement on follow-up assessments (symptom measures and psychophysiological responses) gathered 3, 6 and 12 months post-treatment compared to the patients who receive the placebo.

*Interval specific analyses:* First, the effectiveness of the VRE+DEX treatment will be analyzed for the two interval periods separately: from immediately post-treatment to the 3, 6 and 12 -month assessment. To test these time interval specific treatment effects, logistic regression will be used to compute adjusted odd ratios for dichotomous outcomes and multivariate

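### Hypothesis 1 adjusts for an outcome's own pre-treatment score only if a baseline imbalance screen flags it; always adjusting is a cheap gain in precision

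*Combined protocol and SAP*

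**What the plan says.** Section 10.2, Hypothesis 1, analyses continuous outcomes by multivariate repeated measures ANCOVA. Treatment is the between-subjects factor, with "the pre-treatment vs. post-treatment condition being the within subjects factor, and the scale scores as the multiple measures". The model is described as "accounting for appropriate covariates as determined through preliminary analyses discussed above". On what is read from it, the plan says "Adjusted means and mean differences as well as interaction terms will be obtained and evaluated"; it does not say which term decides.

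The preliminary analyses are in section 10.1, Group Equivalence. Baseline values of the key outcomes are among the variables compared between arms. The selection rule begins "Any observed differences that approach statistical significance", sets the threshold at P ≤ 0.15, and adds a second condition: those "which are theoretically or empirically identified as potential confounders will be included as covariates in subsequent cross sectional and longitudinal analyses". A baseline score must therefore pass both conditions to enter the Hypothesis 1 model as a covariate.

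Section 10.2, Hypothesis 2, differs. In its interval-specific analyses each outcome's baseline value is always a covariate.

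Section 8.0 schedules the symptom scales, and startle, skin conductance, heart-rate and cortisol reactivity to the VR scenes, both before and after treatment. SUDs and the other within-session measures have no matching pre-treatment value. They have their own sentence in the plan ("Average and peak values of these continuous variables will also be analyzed using a repeated measures ANCOVA") and lie outside this point.

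**The concern.** A baseline score is worth adjusting for because it correlates with the outcome, not because randomisation happened to leave the arms unequal on it. Under the 10.1 rule, chance imbalance decides: with one baseline score, the P ≤ 0.15 condition is met in about 15% of randomised trials. In the rest the score stays out as a covariate, and for one scale the group-by-time test is a t-test on change. The rule also leaves the form of the Hypothesis 1 model open until baseline data have been seen.

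What is at stake is precision in the comparison on which the trial was sized, using scores that are already collected. The plan already adjusts for baseline in the Hypothesis 2 interval analyses.

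**Working it through.** **Inputs from the plan (section 10.2, Power and Sample Size).** Two-sided alpha 0.05; d = 0.65; power at least 85%; 50 per arm; 10% lost to measurement by the end of treatment, so 50 × 0.90 = 45 per arm.

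**Assumed, because the documents do not give them.** Pre/post correlation r = 0.3, 0.5, 0.7; ratio k = SDpost/SDpre, taken as 1 unless stated; d on the post-treatment SD; normal data.

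**Step 1: the plan's own figure.** n per arm = 2(1.960 + 1.036)²/0.65² = 42.5, so 43 (44 by noncentral t). Allowing for 10% loss gives 48 or 49 per arm, 96 to 98 in total, against the stated 100. Power at 45 per arm is 86.2%. The figure reproduces, and it belongs to about 45 measured patients per arm.

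**Step 2: the two tests for one scale.** In units of the post-treatment SD with k = 1, the change score has SD √(2(1−r)), and the baseline-adjusted residual has SD √(1−r²).
- r = 0.3: 1.183 against 0.954
- r = 0.5: 1.000 against 0.866
- r = 0.7: 0.775 against 0.714

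For general k the large-sample variance ratio, ANCOVA to change score, is k²(1−r²)/(1+k²−2rk). It never exceeds 1 and equals 1 only when rk = 1. At k = 1 it reduces to (1+r)/2, that is 0.65, 0.75 and 0.85.

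**Step 3: power at 45 per arm, d = 0.65, k = 1.** There were 100,000 simulated trials per setting. Under the rule, ANCOVA is used if the baseline t-test gives P ≤ 0.15 and the change score otherwise, with baseline assumed to meet the confounder condition.

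| r | Change score | P ≤ 0.15 rule | Always adjusted | Gain over change score | Gain over rule |
|---|---|---|---|---|---|
| 0.3 | 73% | 77% | 89% | 15.5 | 11.9 |
| 0.5 | 86% | 88% | 94% | 7.7 | 5.5 |
| 0.7 | 98% | 98% | 99% | 1.2 | 0.7 |

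A noncentral t calculation averaged over chance baseline imbalance agrees: 73.1/86.2/97.6% for the change score and 88.8/93.8/98.9% always adjusted. With no treatment effect the rule rejects in 3.4/3.8/4.2% of trials; never or always adjusting gives about 5%.

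**Step 4: sensitivity, one scale, 45 per arm** (r = 0.3/0.5/0.7).
- k = 0.8: gain 26.6/17.9/6.4 points over the change score, 21.7/13.3/3.9 over the rule.
- k = 1.3: 6.9/1.9/0.0 and 5.1/1.3/0.0.
- k = 1.5: 4.2/0.5/−0.1 and 3.2/0.4/0.0.
- d = 0.50 (the plan's smallest worthwhile difference), k = 1: change score 51/65/86%, rule 53/67/87%, always adjusted 68/77/90%.
- d defined on the change-score SD, k = 1: change score 86%, always adjusted 96/94/91%.

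**Step 5: the joint test.** Five scales (CAPS, PSS, PCL, BDI, STAI), inter-scale correlation 0.6 assumed, the same d on each. The comparison is Hotelling T² on change scores against MANCOVA of post-treatment scores on all five baselines.
- 45 per arm, d = 0.65, k = 1: 65/81/97% against 82/90/98%.
- 45 per arm, d = 0.65, k = 1.3: 75.7/88.4/98.5% against 82.6/89.6/97.9%.
- 37 per arm, d = 0.50, r = 0.7, k = 1.3: about 78% against 74 to 75%.
- 37 per arm, d = 0.65, r = 0.5, k = 1.5: 82.3% against 80.0%.

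With five baselines screened, at least one enters in about 42% of trials. The gain of always adjusting over the rule at 45 per arm and d = 0.65 is then 12.4/5.6/0.6 points at k = 1, 4.8/0.5/−0.3 at k = 1.3 and 2.0/−0.9/−0.6 at k = 1.5.

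**The case against.** The strongest reply is that nothing here is invalid. The change-score test holds its error rate. In the case modelled the rule errs slightly on the conservative side. The trial is labelled a pilot with exploratory aims. All of that is true, and it limits the point to efficiency. It does not remove the point, because the plan sets out two-sided hypothesis tests and a power target, and the remedy uses data already in hand.

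A second reply is that equal SDs flatter the comparison. Entry requires current PTSD on the CAPS, which may narrow the baseline spread, and response to treatment may widen the later spread. The documents give no SDs, so this is an inference, but it is plausible, and at ratios of 1.3 or more the gain largely disappears once r reaches 0.5. This stands as a limit on the size of the gain. A third reply, that the planned test is multivariate and adjustment can cost it power, also stands and is counted in the cost.

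A reader might infer that the completer analysis falls short of the plan's target. The plan states "Initial data analyses will be conducted on treatment completers" and expects attrition "resulting in 25% of participants randomized to placebo or 0.5mg DEX groups that would not complete treatment", which leaves about 37 per arm. There, at r = 0.5, equal SDs and d = 0.65, power is 79% for the change score and 88% always adjusted. The documents do not support using 85% as the yardstick: the power section counts as lost only those not measured, and sets them apart from those who stop treatment. The 85% therefore belongs to about 45 per arm, where the change score already reaches 86% at r = 0.5. The lower figure in completers comes from the analysis set; an unadjusted test of post-treatment scores also has 79% there.

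**Conclusion.** The point holds as a cheap improvement. Hypothesis 1 has no standing baseline covariate, while the Hypothesis 2 interval analyses do. For one scale at 45 per arm, d = 0.65 on the post-treatment SD, equal SDs and r from 0.3 to 0.7, always adjusting adds about 1 to 16 power points over the change score and about 1 to 12 over the rule. The gain is larger when the post-treatment SD is the smaller one, and about zero when it is 1.3 or more times the pre-treatment SD and r is high.

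This rests on assumed r, SDs and scale of d, and on group-by-time being the deciding term, which the plan does not state.

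Two stronger readings are not supported. The first is bias or an inflated error rate: none appears with one outcome and one covariate, although selecting several empirically identified confounders was not modelled. The second is that the plan ignores baseline: the pre-treatment score is already in the Hypothesis 1 model as a response, and the interval analyses adjust for it.

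**What to change.** For each continuous Hypothesis 1 outcome measured before and after treatment (the symptom scales, and startle, skin conductance, heart-rate and cortisol reactivity to the VR scenes), state that the deciding test is the treatment coefficient in an ANCOVA of the post-treatment score. That outcome's own pre-treatment score is always included, whatever imbalance is observed. This matches the covariate rule already written for the Hypothesis 2 interval analyses. In these analyses only, take the outcome's own baseline out of the P ≤ 0.15 screen. SUDs, other within-session measures and the remaining analyses are unaffected.

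If the joint test is kept, use post-treatment scores as the outcomes and the baseline scores as covariates. If separate ANCOVAs replace it, say so, and state which outcome decides or how multiplicity is handled.

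The cost is SAP wording and one degree of freedom per baseline score, with no new data. A single-scale test loses at most about 0.5 power points. A five-scale joint test can lose about 2 to 4 points when the post-treatment SD exceeds the pre-treatment SD and r is moderate to high, so the choice between joint and separate tests should be made with that in view.

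### Hypothesis 1 names no deciding contrast in its pre/post model; it should rest on one, the post-treatment difference always adjusted for that outcome's baseline

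*Combined protocol and SAP*

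**What the plan says.** Section 10.2, under Hypothesis 1, analyses continuous outcomes by a multivariate repeated-measures ANCOVA. Treatment is the between-subjects factor, with "the pre-treatment vs. post-treatment condition being the within subjects factor". On what is read from that model, the plan says: "Adjusted means and mean differences as well as interaction terms will be obtained and evaluated". No term is named as decisive, and it is not stated whether the mean differences are taken over both visits or at post-treatment.

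The sample-size text in the same section points to one visit: "We first calculated the number of participants needed to test the effect of VRE augmentation with DEX at immediate post-treatment assessment (Hypothesis 1 above". It also states "We set the Type I Error rate at 0.05 (two-tailed) for all computations", and gives 50 per group for a "minimum desired power of 85% to detect an effect size of" 0.65. Hypothesis 1 itself predicts greater improvement on DEX, which reads as a statement about change.

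Covariates come from section 10.1 (Group Equivalence). A variable is adjusted for if its baseline difference has P ≤ 0.15 and it is also identified as a potential confounder. By contrast, the interval-specific analyses for Hypothesis 2 always include the outcome's baseline as a covariate.

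**The concern.** A two-group, two-visit model yields several different treatment contrasts for one scale:

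- the treatment effect averaged over the pre and post visits;
- the treatment-by-visit interaction, which is the difference in change;
- the difference at post-treatment, unadjusted or adjusted for baseline.

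The averaged effect is a poor test of Hypothesis 1. Half of it comes from the pre-treatment visit, where randomisation makes the true difference zero. It therefore estimates half the drug effect plus chance baseline imbalance.

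If the plan does not say which contrast decides, the same data on the same scale can be reported as supporting or not supporting DEX, depending on the term read. Power then depends on that choice, and the 5% error rate is not guaranteed. This arises within a single scale, before any question of how many outcomes are tested.

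**Working it through.** **Inputs from the documents.** Two-sided alpha 0.05; 50 per arm; 10% lost to measurement by the end of treatment, so 50 × 0.90 = 45 per arm; planned standardised difference d = 0.65; smallest clinically meaningful difference 0.5 (section 10.2).

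**Assumed, not in the documents.** Pre/post correlation r = 0.3, 0.5, 0.7; equal SDs at both visits, scaled to 1; one scale at a time. The plan's multivariate test across scales is not modelled.

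**Step 1: reproduce the plan's figure.** A two-sample t-test at d = 0.65 needs 44 per arm for 85% power. Allowing for 10% loss, 88/0.90 = 97.8, or 98 in total, against the stated 100. At 45 per arm power is 86.2%. The figure reproduces as a simple comparison of post-treatment means.

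**Step 2: power of each candidate contrast.** For a standardised effect δ, the noncentrality is δ × √(45/2) = 4.743δ, on about 88 degrees of freedom.

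- Averaged effect: δ = (d/2)/√((1+r)/2). At r = 0.5, 0.325/0.866 = 0.375, noncentrality 1.78.
- Interaction: δ = d/√(2(1−r)). At r = 0.5, 0.65/1 = 0.65, noncentrality 3.08.
- Post-treatment, unadjusted: δ = d = 0.65.
- Post-treatment, baseline-adjusted: δ = d/√(1−r²). At r = 0.5, 0.65/0.866 = 0.751, noncentrality 3.56.

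| Contrast (45 per arm, d = 0.65) | r = 0.3 | r = 0.5 | r = 0.7 |
|---|---|---|---|
| Averaged over visits | 47% | 42% | 38% |
| Treatment-by-visit interaction | 73% | 86% | 98% |
| Post-treatment, unadjusted | 86% | 86% | 86% |
| Post-treatment, baseline-adjusted | 89% | 94% | 99% |

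At d = 0.5 the levels drop: 31, 27, 25% averaged; 51, 65, 86% interaction; 65% unadjusted; 69, 77, 91% adjusted. The adjusted post-treatment difference remains the most powerful at each r.

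**Step 3: how often the terms disagree when d = 0.65** (simulation, 45 per arm, no baseline covariate). Averaged effect against interaction: opposite decisions in 51, 56, 62% of trials. Interaction against the post-treatment difference: 14 to 23% unadjusted, 2 to 19% adjusted.

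**Step 4: false-positive rate for one scale if any significant term counts.** With equal variances, the averaged effect and the interaction are independent under the null, so the chance that at least one is significant is 1 − 0.95² = 9.75%. The other readings below are simulated over r = 0.3 to 0.7.

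| Terms allowed to count, and covariate handling | Rate |
|---|---|
| Averaged or interaction, baseline not a covariate | about 9.75% |
| Those two or the adjusted post-treatment difference, baseline not a covariate in the two-visit model | 10.6–11.4% |
| Interaction or unadjusted post-treatment difference | 8.8–9.4% |
| Interaction or adjusted post-treatment difference | 6.8–7.8% |
| Averaged or interaction, baseline always a covariate | 5% |
| Averaged or interaction, baseline a covariate whenever its P ≤ 0.15 | 4.4–4.7% |
| As the row above, plus the post-treatment difference under the same covariate rule | about 6% |

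The 5% row is exact. With the pre score as covariate, the average (pre + post)/2 and the change (post − pre) both reduce to post-treatment adjusted for pre, so the two tests are the same test. The last two rows assume that an imbalanced baseline score always counts as a potential confounder.

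**The case against.** A reader might infer that the plan's false-positive rate for a scale is 10 to 11% rather than 5%. The documents do not support that. They say the terms will be evaluated, not that any one significant term is enough. They never say that an average over pre and post tests efficacy; the sample-size text and the predicted result both point to post-treatment or change. And the model is an ANCOVA whose covariates come from section 10.1. If that rule brings in the scale's own baseline at P ≤ 0.15, the averaged-or-interaction rate is about 4.4 to 4.7%. So the error rate cannot be discussed apart from baseline adjustment. This part of the objection stands.

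It does not remove the point. Under randomisation about 85% of trials will not meet P ≤ 0.15 for a given scale, so baseline would usually stay out. Even with the rule applied in the way most favourable to the plan, the averaged effect has only 45 to 53% power at d = 0.65 and disagrees with the interaction in 39 to 54% of trials. If the averaged effect is set aside, the interaction and the post-treatment difference still differ in power and can disagree.

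It can also be said that this is a pilot with exploratory aims. But the summary describes a randomised, placebo-controlled efficacy study, and section 10.2 predicts significant differences and states alpha and power. A named contrast is a fair request.

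**Conclusion.** The concern holds in a limited form. The Hypothesis 1 analysis does not name its deciding contrast, and the outcome's own baseline enters only conditionally, although it always enters the interval-specific Hypothesis 2 analyses.

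The firm consequence is for power and interpretation. Depending on the term read, power at the planned effect runs from 38% to 99% for r between 0.3 and 0.7. Without the averaged effect the range is 73% to 99%. These figures rest on 45 per arm and d = 0.65 from the plan, and on the assumed correlation and equal SDs.

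The consequence for false positives is conditional. About 10 to 11% needs all three of an any-term-counts rule, the averaged effect among the deciding terms, and no baseline covariate. Other readings give about 4 to 9%. The plan neither states nor excludes the any-term rule, so the upper figure is a possibility to close off and not the plan's error rate.

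**What to change.** In section 10.2, Hypothesis 1, replace the sentence on what will be evaluated with:

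> For each continuous outcome, Hypothesis 1 is tested by one contrast: the DEX minus placebo difference at the post-treatment visit, adjusted in every case for that outcome's pre-treatment score, at two-sided alpha 0.05. Adjusted means, the treatment effect averaged over visits and the treatment-by-visit interaction are reported as descriptive only.

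This matches the contrast used for the sample size, uses data already collected, and follows the baseline adjustment already planned for the interval-specific Hypothesis 2 analyses. Within each scale it fixes the error rate at 5% and gives 89 to 99% power under the assumptions above. Naming the interaction instead would also settle the ambiguity, but its power is 73% at r = 0.3, below the 85% target, and lower than that of the adjusted difference at every correlation considered.

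The cost is one sentence, with no new patients or data. The small downside is that the sponsor gives up the other terms as evidence of efficacy.

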#### Measures at each Therapy Session

Expectancy of Therapeutic Outcome Questionnaire (ETOQ) assesses how logical the treatment appears, and the expectancy of success for the patient and for others. This measure is administered after session 1 only.

Clinical Global Impressions Scale, Severity of Illness (CGI-Severity; Guy & Bonato, 1970). This is a study personnel rated measure of severity of illness ranging from 0 (not assessed) to 7 (among the most extremely ill patients). This measure is administered after sessions 1–6.

Clinical Global Impression – Improvement (CGI-Improvement; Guy & Bonato, 1970). This is a study personnel rated measure of patient's improvement since start of study ranging from 1 (very much improved) to 7 (very much worse). This measure is administered after sessions 2-6.

Clinical Global Improvement Scale, Patient Report (CGI - Self Report; Guy & Bonato, 1970). This is a self-reported global measure of change in severity of symptoms, ranging from 1 (*very much improved*) to 4 (*unchanged*) to 7 (*very much worse*). This measure is administered after sessions 1-6.

The PTSD Symptom Scale is a 17-item interview used to aid in the detection and diagnosis of PTSD (described above), administered before sessions 2-6.

Subjective Units of Discomfort (SUDs) will be gathered during each exposure session (sessions 2-6). Participants will be asked to rate their level of discomfort on a scale of 0 (no anxiety) to 100 (panic levels of anxiety) every 5 minutes during the VR exposure.

Intent to Attend (Leon et al., 2007) is a short, two question survey asking participants how likely they are to complete all of the study and how likely they are to attend the next session.

Blinded Medication Check is a one-question measure to assess which medication the participant believes they took.

Cortisol Sampling will be obtained from saliva in order to measure post-dexamethasone cortisol levels and detect the presence of dexamethasone in saliva. Cortisol sampling methods are described below.

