#### Post treatment and 3, 6 and 12-month Follow-up Assessments

The Clinician Administered PTSD Scale (CAPS) (see above).

The Beck Depression Inventory (BDI) as above.

The PTSD Symptom Scale as above.

The Clinical Global Improvement Scale (Severity, Improvement, and Patient Report) as described above.

The Quality of Life Inventory as above.

The State Trait Inventory as above.

Patient Update Interview: This a brief study personnel-interview administered to obtain general patient follow-up data, i.e. between-assessment treatment, medication changes, substance use status/changes, and patient report on relationship/employment/health changes.

Psychophysiological Patient Report as above.

Psychophysiological and Cortisol Reactivity (as described above) to the VR scenes will be assessed at each follow-up point.

Posttraumatic Stress Disorder Checklist (PCL) as above.

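### The two 7-point CGI change ratings cannot enter the pre/post ANCOVA, so Hypothesis 1 tests them only as a yes/no cut, at a cost of about 13–20 points of power under assumed distributions

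*Combined protocol and SAP*

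**What the plan says.** Section 10.2 (Hypothesis 1) analyses continuous outcomes by a multivariate repeated measures ANCOVA, with "the pre-treatment vs. post-treatment condition being the within subjects factor, and the scale scores as the multiple measures". As an additional approach it names two categorical measures of clinically significant improvement. One is a 30% fall in CAPS. The other is a CGI rating of *much* or *very much improved*, with the raters and the method given as follows: "by the therapist and participant on the CGI inventory at the end of active treatment. These data will be analyzed using logistic regression".

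Section 8.0 defines the ratings. Under Measures at each Therapy Session, CGI-Improvement is described thus: "This is a study personnel rated measure of patient's improvement since start of study ranging from 1 (very much improved) to 7 (very much worse". It is taken after sessions 2–6. The patient report is also a 1-to-7 rating of change, with 4 meaning unchanged, taken after sessions 1–6. The Pre-Treatment Assessment lists CGI-Severity and no improvement rating. At post-treatment and at 3, 6 and 12 months all three are collected: "The Clinical Global Improvement Scale (Severity, Improvement, and Patient Report) as described above".

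The sample-size text states "We set the Type I Error rate at 0.05 (two-tailed) for all computations", and gives 100 participants "to achieve a minimum desired power of 85% to detect an effect size of" 0.65. It takes half a standard deviation as the effect that "is the smallest clinically meaningful difference between DEX-augmented VRE vs. placebo-augmented VRE at the end of treatment".

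**The concern.** CAPS is measured before and after treatment, so its responder cut sits beside a full-scale analysis in the ANCOVA. The two CGI change ratings have no such counterpart. They rate change since the start, so no pre-treatment level exists for a model whose within-subject factor is pre versus post. The patient report does have a value after session 1, before the first study pill, but that is a change rating made after randomisation and not a pre-treatment level.

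The cut is therefore the only stated Hypothesis 1 test of these ratings. It treats levels 1 and 2 alike, and it treats unchanged (4) and very much worse (7) alike. A real difference on the change ratings could go undetected because of how they were scored, although the full ratings are already collected. The plan also does not say whether therapist and participant must both report improvement, or whether each rating is tested separately.

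**Working it through.** **Inputs from Section 10.2.** Two-sided alpha 0.05; d = 0.65 for the sample size; d = 0.50 as the smallest meaningful difference; 50 per arm; 10% lost to measurement by the end of treatment, so 50 × 0.9 = 45 per arm.

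**The plan's own figure.** For a difference in means, power ≈ Φ(d√(n/2) − 1.96).
- 50 per arm: 0.65 × √25 − 1.96 = 1.29, giving 90.2% (t-test 89.6%).
- 45 per arm: 0.65 × √22.5 − 1.96 = 1.123, giving 86.9% (t-test 86.2%).

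The stated 85% is reproduced once the 10% loss is applied. It refers to a difference in means.

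**Assumptions for the CGI.** The documents give no CGI distribution or responder rate. Assumed: a latent normal rating, shifted by d in the DEX arm and cut into seven levels 0.7–1.0 SD apart, with a placebo responder rate (levels 1–2) of 20–80%. Applying d = 0.65 to the latent CGI rating is itself an assumption.

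**One setting by hand.** With placebo rate p0, the DEX rate is p1 = Φ(Φ⁻¹(p0) + d). For p0 = 0.30, p1 = Φ(−0.524 + 0.65) = 0.55. The mean rate is 0.425.
- Null SE = √(2 × 0.425 × 0.575/45) = 0.1042.
- Alternative SE = √((0.30 × 0.70 + 0.55 × 0.45)/45) = 0.1008.
- Power = Φ((0.25 − 1.96 × 0.1042)/0.1008) = Φ(0.454) = 67.5%.

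**Simulation.** At least 10,000 trials per setting, 45 per arm, one rating, no covariate. The ordinal test is the tie-corrected Wilcoxon test, which is the score test of the proportional-odds model. The cut is tested by the logistic likelihood ratio. Results for d = 0.65, with ranges covering the two spacings and repeated runs:

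| Placebo responder rate (assumed) | Ordinal test | Responder cut | Loss, points |
|---|---|---|---|
| 20% | 82–84% | 65–66% | 16–18 |
| 30% | 82–83% | 66–67% | 15–17 |
| 50% | 80–81% | 66–67% | 13–15 |
| 70% | 75–78% | 57–59% | 16–20 |
| 80% | 69–74% | 48–49% | 20–26 |

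At d = 0.50 the loss for placebo rates of 20–70% is about 13–18 points. With no treatment effect both tests stay near 5%.

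**A different pattern of effect.** Suppose the placebo distribution over levels 1–7 is 10/25/30/25/7/2/1%, and DEX moves 25–30% of patients from levels 3–4 to level 2 and changes nothing else. The responder rate then rises from 35% to 60–65%. The cut has about 65–82% power and the ordinal test about 39–55%. This pattern is also an assumption, but it reverses the sign.

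**The case against.** The strongest case on the other side has four parts.

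- **Weight.** The responder test is an additional approach in a pilot with exploratory aims. The first analysis is of the continuous symptom and psychophysiological measures, and no decision depends on the CGI cut. This stands. A reader might infer that the trial falls short of its 85% power. The documents do not support that: the 85% was never claimed for the CGI, and it is reproduced for a difference in means.
- **CGI-Severity.** It is rated before and after treatment and can enter the ANCOVA on its full scale. This stands. A reader might infer that the plan has no full-scale CGI analysis at all, but that is true only of the two change ratings.
- **The gain is built into the model.** A uniform latent shift favours a rank test, and an effect concentrated at the threshold favours the cut. This stands too, and it rules out saying that the ordinal test is always better or that the responder result should be dropped.
- **The cut asks a different question.** Clinically significant improvement is a legitimate target and easy to read. That supports keeping the cut, but not leaving it as the only analysis of these ratings.

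A reader might also extend the point to follow-up. Section 10.2 states this cut only for the end of active treatment, so the point is confined to Hypothesis 1.

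**Conclusion.** The structural point holds on the documents alone: two 7-point change ratings, no pre-treatment value, an ANCOVA that needs one, and a responder cut as the only stated Hypothesis 1 analysis.

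The size rests on assumptions. With a latent normal shift of 0.65, 45 measured per arm and a placebo responder rate of 20–70%, the cut has about 57–68% power against about 75–84% for an ordinal test, a loss of about 13–20 points. Losses of 20–26 points appear only at an assumed 80% placebo rate and should not be quoted as typical. If the effect sits at the responder threshold, the loss becomes a gain.

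This is a low-cost improvement to a supplementary analysis. It is not a defect in the trial's main comparison.

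**What to change.** In Section 10.2, Hypothesis 1, pre-specify for the post-treatment CGI-Improvement rating and the post-treatment patient report, each separately, a proportional-odds model on the full 7-point scale. Treatment arm is the tested term and pre-treatment CGI-Severity the covariate. Report the common odds ratio with its 95% CI.

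Keep the proportion *much* or *very much improved* by arm, with its odds ratio and CI, as a supportive measure of clinically significant improvement. Report it for each rater separately, which also settles how the two ratings are used. The two ratings need not be summed. The CAPS responder analysis can stay as it is.

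The cost is a few sentences in the plan and a few lines of code, with no new data, visits or participants. Two downsides should be stated in the plan: the model assumes roughly proportional odds across levels, and the cut could have more power if the drug effect were concentrated at the responder threshold. The second is the reason for retaining the responder result.
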